#### 7.2 Sample size

The study will be complete when there is full data for 36 participants meeting inclusion criteria.

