#### 7.6 Withdrawal

Participants are free to withdraw at any time up to the end of data analysis, without affecting their clinical care or association with the University, and do not need to give a reason for this to the investigators.

Rarely, it may be necessary for participants to withdraw from the study if they feel unwell or there is a concern from one of the study team. If this happens, the PI will discuss with the participant the reasons for withdrawal and any future plans to ensure that the participant's wellbeing is maintained.

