#### 7.7 Replacement of Participants

Participants who discontinued from the study may be replaced.

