#### 8.6 Participant remuneration

Participants will receive £100 for completing the study, and up to £25 for travel expenses throughout the study. Ineligible participants at screening or participant withdrawals before the end of the study will receive £10 remuneration.

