The dose of prucalopride will be titrated with 1mg for 2 days, followed by 2x1mg for the remainder or the study. All participants will received a check-in from the study team at day 2 and 4. If participants are experiencing side effects at the day 2 check-in (before potential dose escalation) or day 4 check-in (after potential dose escalation), a clinician on the study team will be contacted to discuss the best management plan for the participant. Dose escalation for prucalopride in this manner has been found to be very well tolerated, including in participants who are antidepressant – naïve (as determined by the PROGRESS study). Side effects will be formally checked at baseline and study end using the side effects checklist.

Reports of adverse events which are reported by the participant and/or study team member(s) as possibly having been caused by the study activities (e.g. distress during interview, or because of interaction with study team) will include separate individual assessment of seriousness and causality. We will also report these as required using the Yellow Card Scheme: www.mhra.gov.uk/yellowcard.

Adverse events and serious adverse events will be recorded, investigated, and reported as per the Standard Operating Procedure (UoB SOP: ADVERSE EVENT REPORTING, V2.0, 20.1.2023).

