## Data Management

#### 16.1 Sample size calculation

Previous studies investigating the effect of prucalopride / other serotonergic drugs on acute cognition assessed with behavioural measures indicate an effect size of 0.8-0.9 may be expected. As relatively little is known about 5-HT4R stimulation in healthy participants we PLEs, we conservatively estimated a smaller effect size (0.5-0.7) for sample size calculation. This indicates 15-17 participants/group would give 85-90% power to detect a significant group difference at a 0.05 false positive rate. We aim to recruit up to 36 (18 in each group) to allow for withdrawals and exclusions for data quality reasons.

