#### 16.3.2 Participant log and link key

A screening log of all potential participants will be maintained. This will include potential participants who were considered but later deemed ineligible due to meeting one of the exclusion criteria or withdrew. The reasons for exclusion or refusal will also be recorded against their ineligibility / refusal status. This log will be stored securely on University of Birmingham servers. For participants who withdraw up to the end of data analysis, their data will be withdrawn. It will not be possible to withdraw data, once data analysis has completed. This will be communicated in the PIS.

All participants who are considered for or enrolled in the study will receive an individual identification number (Participant ID). Documentation regarding potential participants and participants enrolled in the study will only be accessible to study team members who need this information for conducting the study. All data collection will use the Participant ID to link the data to one individual. The key that links Participant ID and participant names will be stored on secure University of Birmingham servers and will be kept until publication of the study.

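### Section 16.3.2 removes the data of every participant who withdraws, so the protocol as written leaves only completers to analyse and does not exempt safety records

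*Protocol*

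**What the plan says.** Five parts of the protocol bear on this point.

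- **Section 16.3.2** sets the data rule: "For participants who withdraw up to the end of data analysis, their data will be withdrawn". It adds that removal is impossible once analysis has finished and that the information sheet will say so. The same section keeps a screening log that includes people who withdrew.
- **Section 7.6** allows withdrawal until the end of data analysis and, under the same term, says "it may be necessary for participants to withdraw from the study if they feel unwell" or if the study team is concerned.
- **Section 7.7**: "Participants who discontinued from the study may be replaced".
- **Section 7.2**: "The study will be complete when there is full data for 36 participants meeting inclusion criteria". Section 16.1 puts the target differently: "We aim to recruit up to 36 (18 in each group) to allow for withdrawals and exclusions for data quality reasons".
- **Section 11**: "Adverse events and serious adverse events will be recorded, investigated, and reported" under a standard operating procedure. Sections 15.1 and 15.2 add medical review and minuted review of adverse-event forms. Section 11 also says the side-effects checklist is completed at baseline and study end. Section 17.1 compares it between groups.

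On payment, section 8.6 gives £100 for completing the study, while "participant withdrawals before the end of the study will receive £10 remuneration".

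**The concern.** A randomised comparison is protected by keeping everyone in the arm to which they were assigned. Here the protocol prescribes removal, and the reason for leaving makes no difference. A participant who leaves because they feel unwell, which is a plausible effect of treatment, falls under the same rule as one who moves away or asks for their data to be erased.

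Three things are at stake. The first is the primary cognitive comparison, which becomes a comparison of people who stayed. The second is the side-effect-checklist comparison, which loses the people most likely to have had side effects. The third is safety accounting, because section 11 promises to record and report events while section 16.3.2 removes the data of those who leave, with no exemption.

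Section 5.3 says the study will supply an effect-size estimate for the next trials, so any selection effect would carry forward into their design.

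**Working it through.** **Step 1. What the text does to each kind of leaver.**

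| Event | What the protocol says | What remains to analyse |
|---|---|---|
| Leaves before Visit 3 because unwell | Withdrawal (7.6); data removed (16.3.2); may be replaced (7.7) | Nothing, including baseline |
| Completes Visit 3, withdraws before analysis ends | Withdrawal still allowed (7.6); data removed (16.3.2) | Nothing, although both visits exist |
| Stops capsules but would attend Visit 3 | Not addressed as a separate event | Unclear |

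The resulting data set consists of people with full data who did not withdraw at any point up to the end of analysis. The SAP is not shown, but an SAP can define populations and missing-data methods only for data that still exist.

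**Step 2. The plan's own allowance for losses.** Section 16.1 needs 15 to 17 per group and recruits 18.

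- Smallest allowance: (18 − 17)/18 = 5.6%, or 2 participants in total.
- Largest allowance: (18 − 15)/18 = 16.7%, or 6 participants in total.

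This covers both arms and includes data-quality exclusions. The protocol gives no expected withdrawal rate overall or by arm.

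**Step 3. Size of a possible shift (assumed inputs).** Let p be the share of the drug arm lost and D the amount, in SD, by which those lost would have scored worse than drug completers. The mean of all assigned is (completer mean − p × D), so analysing completers shifts the difference towards drug by p × D. This assumes no matching loss on placebo.

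| Lost of 18 | p | D = 0.5 | D = 1.0 |
|---|---|---|---|
| 1 | 5.6% | 0.028 | 0.056 |
| 2 | 11.1% | 0.056 | 0.111 |
| 3 | 16.7% | 0.083 | 0.167 |
| 4 | 22.2% | 0.111 | 0.222 |

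Section 16.1 states: "we conservatively estimated a smaller effect size (0.5-0.7) for sample size calculation". Against that effect, the extremes are 0.028/0.7 = 4% and 0.222/0.5 = 44%.

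**Step 4. A second set of assumptions.** Suppose the least tolerant share p of the drug arm is removed and tolerability correlates r with the outcome. The shift is then r × φ(z)/(1 − p), where z is the normal quantile at p and φ the normal density. For r of 0.3 to 0.5 and p of 1/18 to 4/18, the shift is 0.04 to 0.19 SD. With 18 per group and no true effect, a nominal two-sided 5% test would then reject in about 5.1% to 8.6% of trials.

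**Step 5. When there is no shift.** If losses are equal in the two arms and unrelated to outcome, the shift is zero. Once the data have been removed, nobody can check which case applies.

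**Step 6. What keeping data alone would recover.** Visit 3 is the only assessment after baseline (sections 8.1 and 8.2). Keeping an early leaver's baseline data shows who left, but supplies neither a follow-up cognitive score nor an on-treatment checklist. Only attendance at Visit 3 does that. For someone who withdraws after Visit 3, keeping the data recovers everything.

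**The case against.** The strongest reply is that section 16.3.2 is a consent right and not a discontinuation rule. It runs to the end of analysis, long after the last capsule, and the sentences around it concern when data can still be taken out. Section 12 mentions stopping medication (in the event of pregnancy) without calling it withdrawal, and section 11 sends side effects to a clinician and not to the exit. This has force: the protocol does not say that stopping capsules is withdrawal. But the sentence makes removal follow from withdrawing, without any request, and section 7.6 uses the same term for leaving because unwell. The ambiguity is itself what needs correcting.

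A second reply is that most of the lost outcome information comes from ordinary dropout, since an early leaver has no Visit 3 score in any case. That stands, and it is why retaining data is only part of the remedy.

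A third is that populations and missing data belong in the SAP. That holds for methods, but not for a rule that removes the data and is promised to participants in the information sheet.

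Readers might also infer more than the text supports:

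- *The worst side-effect cases disappear.* Sections 11, 15.1 and 15.2 give adverse events their own route of recording, reporting and review. What the text supports is that section 16.3.2 does not exempt those records, and that the checklist comparison loses early leavers.
- *People who tolerate the drug are compared with placebo.* Placebo withdrawals are removed too, replacement is optional, and section 16.1 speaks of recruiting up to 36. Bias needs withdrawal that differs by arm or relates to outcome.
- *The £10 payment discourages reporting of symptoms.* Section 8.6 reduces payment for withdrawing, not for reporting, and does so in both blinded arms. Section 11 also has check-ins at days 2 and 4.

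**Conclusion.** The point holds as a defect in the written rules. Sections 7.2, 7.6, 7.7 and 16.3.2 together produce a completers-only data set and rule out an analysis of all randomised participants. If section 7.2 gives way to the limit in section 16.1, fewer people are analysed, but they are still completers only.

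Bias is a risk and not an established result. The illustrative shift of about 0.03 to 0.22 SD in favour of drug rests on three assumptions absent from the protocol: 1 to 4 losses among 18 on drug, no matching loss on placebo, and leavers who would have scored 0.5 to 1.0 SD worse. Other assumptions give other values, including zero.

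Sections 11 and 16.3.2 must be reconciled whatever the dropout turns out to be.

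**What to change.** Reword sections 7.6, 7.7 and 16.3.2 and the information sheet so that they:

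1. Separate three events: stopping capsules, leaving the visits, and an explicit request to delete data.
2. Keep and analyse data collected up to withdrawal unless the participant explicitly asks for deletion. Always keep allocation and adverse-event records, and say so at consent.
3. Invite participants who stop capsules early to the Visit 3 assessments, pay them for attending, and analyse everyone as randomised.
4. Count replacements as additional to the people they follow, and report withdrawals and reasons by arm. State whether section 7.2 or section 16.1 sets the recruitment limit.

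The cost is one amendment to the protocol and information sheet, plus at most £100 − £10 = £90 for each early stopper who attends Visit 3. The downside is that some Visit 3 data will be off drug, which slightly dilutes the measured effect.

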#### 16.3.3 Safeguards for data collection and storage:

- Source data are documents where the study data are first recorded. This will include the
  eCRF for demographic and interview data, neurocognitive computer task responses, MRI
  data, and blood sample data. As data collected will be personal and potentially sensitive
  data will be retained in a secure location at or by the recruitment site, accessible only to
  delegated study team members and relevant site staff.
- Demographic and interview data (collected on the eCRF) will be stored using secure servers at the University of Birmingham supported logistically by University of Birmingham (UoB).
- Questionnaire data will be stored using an electronic platform (REDCap). There is an
  agreement with REDCap that they will meet and provide us with a database which is specific
  to the requirements of this study and as per CTOC. This data will be downloaded onto
  university secure servers- supported logistically by University of Birmingham (UoB).
- Neurocognitive task and MRI data will be stored and analysed using university secure servers.
- Blood samples will be handled and transported within UoB by study team staff and received, pre-processed, and acellular material stored securely by [name] lab, using Standard Operating Procedures and in accordance with the Human Tissue Act 2004 (UoB SOPS: LABORATORY SET UP AND MANAGEMENT SOP, V3.0, 14.3.2022 (UoB-CRL-SOP-001) & LABORATORY FACILITIES SOP, V3.0, 14.3.2022 (UoB-CRL-SOP-002) & SAMPLE MANAGEMENT SOP, V3.0, 14.3.2022 (UoB-CRL-SOP-003); UoB QCD: LABORATORY ROLES AND DUTIES (UoB-CRL-QCD-002). PBMCs will be stored using the HBRC. Following analysis, the acquired data will be stored on university secure servers as per UoB SOP: LABORATORY ANALYSIS SOP (UoB-CRL-SOP-004).
- Participant IDs will pseudoanonymise data, the link key for which will be stored on the University's secure server until publication.
- Anonymised electronic and blood sample and microbiome data is held for 10 years on the University's secure server (see 15.3.6 Data Archiving) – supported logistically/financially by UoB.

UOB ethics number: ERN\_3117

- Data will only be accessible to the study team with capacity for full audit trail.
- Data stored on University secure servers will have appropriate back-up and security
  measures in place. The study data system will be recorded on the University's data asset
  register, amended accordingly should any amendments to the system be required. Relevant
  staff will be appropriately trained in using the system prior to dealing with the research data
  and of the need for any modifications to the data to be logged (i.e. there is an audit trail).

#### 16.3.4 Data Sharing

Analysis code, and pseudoanonymised quantitative raw and MRI data, along with the protocol and analysis plans will be shared where practicable using repositories such as Open Science Framework and Neurovault. PBMCs will be stored anonymously on the University of Birmingham HBRC archive to serve as an ongoing resource for future research. This will ensure long-term curation of this data, and will be specified in the consent form and Participant Information Sheet.

Personal information will not be shared. The act of pseudoanonymising information will ensure that all personal information about research participants is removed and replaced with a code number. During the study, the research team will have the link key between the participant's personal identifying information (Participant ID) and the coded data should the need to re-identify the participant arises. The PI and study team will keep this link key in a securely protected database.

#### 16.3.5 Protocol Deviations and Suspected/Serious Breaches

Deviations are any (minor or major) breach, divergence or departure from the requirements of Good Clinical Practice or the clinical trial protocol. A protocol deviation is a less serious non-compliance with the approved study protocol. Examples of protocol deviations may include visits / assessments performed early or later than scheduled date. A suspected breach is a possible serious breach of GCP or the protocol which has been identified by a third party. An example of suspected breaches include missing consent forms. A serious breach is a breach of GCP or the protocol that is likely to affect to a significant degree the safety or rights of a study participant, or the reliability and robustness of the data generated in the study. An example of a serious breach is confirmation that informed consent was not obtained.

Any deviations to the data management process will be appropriately managed (according to the UoB SOP: DEVIATIONS AND SERIOUS BREACH REPORTING SOP (UoB-DSB-SOP-001). A serious breach should be notified to [name], Head of Research Governance & Integrity Email: [contact].

#### 16.3.6 Data Archiving

All paper and electronic data including the Trial Master File and trial database will be retained and archived in accordance with University of Birmingham Standard Operating Procedures (UoB QCD: GUIDE TO RETENTION TIMES, v2.0, 21.8.23 (UoB-ARC-QCD-003); UoB SOPs: ESSENTIAL DOCUMENTS DEVELOPMENT AND MAINTENANCE SOP (UoB-ESD-SOP-001) & ARCHIVING, v2.0, 21.8.23) which are compliant with the UK GDPR. This indicates a retention period of 10 years minimum is to be expected.

UOB ethics number: ERN\_3117

#### 17. Statistical Methods

Data analysis will be outlined in the Statistical Analysis Plan (SAP), which will be approved by the study team and uploaded to clinicaltrials.gov prior to analysis. The CI (or their delegate) will lock the data from any further changes once data collection has been completed and the SAP approved to allow for statistical analyses to begin (as per the UoB SOP: Statistics (UoB-STA-SOP-001)).

An outline of planned analysis is given below.

#### 17.1 Analysis plan outline:

#### Questionnaire data

Comparison of ANOVA or linear mixed models to compare groups (prucalopride versus placebo) over two time points (baseline versus follow up) on:

- 1) Questionnaires of psychotic-like experiences (PLE), perceived cognitive deficits (PDQ), mood and anxiety (PHQ-9, GAD-7, SHAPS, visual analogue scale of state affect)
- 2) Side effect checklist

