## 9. Randomisation and Blinding

Drug procurement, & encapsulation will be carried out by an approved external provider sourced through the University of Birmingham: the NHS Scotland Pharmaceutical 'Specials' Service.

The Encapsulation Lead / Regulatory Manager from the Oxford Health Biomedical Research Centre will generate a randomisation list using Sealed Envelope; https://www.sealedenvelope.com (an online randomisation tool established since 2001; ISO 27001 compliant and accredited by UKAS). The University of Birmingham is a partner of the OHBRC and therefore as such is able to make use of their facilities and resources. Sealed Envelope is a well established web-based randomisation tool that has been used and cited in numerous peer-reviewed papers, including a published experimental medicine study by this proposed study's PI ([name] et al., The effect of the 5-HT4 agonist, Prucalopride, on functional magnetic resonance imaging faces task in the healthy human brain. Frontiers Psychiatry (2022) 13:859123). The list will be randomised against 2 treatment groups (placebo vs drug) and stratified according to gender (male vs female). Randomisation will be blocked in design (Blocks of 4) to ensure even distribution of treatment allocations for every 4 stratified participants.

Drug & placebo encapsulation and labelling will subsequently be carried out using this randomisation list according to the NHS Scotland Pharmaceutical 'Specials' Service SOP signed by a Qualified Person (QP). In summary, drug tablets and placebo are over-encapsulated in matched capsules. This is led by their Encapsulation Lead and carried out by 2 people such that each part of the encapsulation process is double checked. Encapsulation is carried out on 'clean' benches in designated rooms, by personnel wearing PPE to prevent contamination of the encapsulated drugs. Correct number of either prucalopride or placebo capsules are counted into labelled bottles according to the blinded randomisation list. Bottles are labelled numerically with gender identifiers e.g. F01, F02 for the first two female participants, M01, M02 for the first male

UOB ethics number: ERN\_3117

participants. Thus labelling with these unique identifiers enable the capsule contents to remain blinded to the participants and study personnel.

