## 12. Risk Mitigation

A project-specific risk assessment has been performed and is documented below as per Standard Operating Procedure (UoB SOP PROJECT OVERSIGHT & QUALITY MANAGEMENT: UoB-POS-SOP-001, V3.0, 8.1.2024).

- Risk: Potential for insufficient recruitment from the community
   Mitigation: We have allowed additional time (3 months) for recruitment in our study plan to allow for
   slower recruitment in some months (estimated 1-2 participants per months after data collection
   starts). We are also co-producing recruitment materials with specifically recruited Birmingham YAG
   members to ensure that our participant-facing materials are as inclusive as possible and are attractive
   to the community.
- Risk: It is possible that some participants may find it difficult to understand instructions regarding study processes.
   Mitigation: We will give these both verbally and in written form, and will check understanding prior to study procedures.
- 3. Risk: It is possible that participants may have varying sub-clinical cognitive and mood differences at recruitment, which may impair our ability to detect signal in neurocognitive measures.

UOB ethics number: ERN 3117

Mitigation: We will assess baseline mood and subjective cognitive difficulties, and we can incorporate these into analytical models as necessary to account for subclinical differences in cognition and mood.

[figure not shown]
- 4. Risk: Participants may deteriorate in terms of mental state during the course of the study. Mitigation: As the study is short, and involves only healthy volunteers, this is unlikely to occur. However, we will monitor the results of the SCID at screening, and the PHQ-9, GAD-7 and PLE during each study visit. Any concerns will be discussed with the PI and / or supervising medical investigators, all of whom are psychiatrists with experience in managing patients with serious mental illness and suicidal thoughts and behaviours. We will also ask all participants to provide the details of a GP or other health professional so that the study team can advise them of their participation in the study
- 5. Risk: Bias from accidental unblinding Mitigation: To preserve the blind, prucalopride and placebo will be encapsulated to appear identical and labelled blinded. The randomisation list will be generated by an independent pharmacist and access to the unblinded code list will be restricted to the randomisation service provider.

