#### Behavioural neurocognitive testing (excluding FERT)

Comparison of ANCOVA or linear mixed models to compare groups (prucalopride versus placebo) over two time points (baseline versus follow up).

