#### **FERT**

As in previous work [21, 22], FERT data will be analysed using repeated measures analyses of variance (ANOVAs). Group (prucalopride or placebo) will be the between-subject factor, and emotion (6 levels) will be the within-subject factor.

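### Two-visit questionnaire models amount to a change-score test, FERT has no baseline term, and the gender stratum is in no outlined model: precision is given up that one ANCOVA would recover

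*Protocol*

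**What the plan says.** Protocol section 17.1 outlines the models.

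- **Questionnaires:** "Comparison of ANOVA or linear mixed models to compare groups (prucalopride versus placebo) over two time points (baseline versus follow up) on" PLE, PDQ, PHQ-9, GAD-7, SHAPS and a visual analogue scale, plus the side effect checklist.
- **Cognitive tasks other than FERT:** "Comparison of ANCOVA or linear mixed models to compare groups (prucalopride versus placebo) over two time points (baseline versus follow up").
- **FERT:** a repeated-measures ANOVA in which "Group (prucalopride or placebo) will be the between-subject factor, and emotion (6 levels) will be the within-subject factor". No time factor and no baseline score is named.
- **Resting-state fMRI:** the network and seed group-level models list the two treatment groups and their contrasts.

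Section 9 says that the randomisation list is "stratified according to gender (male vs female"), in blocks of four. None of the models above contains gender. Section 12 says of baseline mood and subjective cognition that "we can incorporate these into analytical models as necessary to account for subclinical differences in cognition and mood".

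Section 8.5 makes neurocognitive task performance primary, and subjective cognition, mood and anxiety secondary. Sections 16.3.1 and 17 defer the detail to a SAP, to be documented in advance and posted before analysis. Section 17.1 is described there as an outline.

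**The concern.** With at most 18 people per group, the analysis should use the information that the design already collects. Each scale and task is measured before treatment, and gender is known and balanced by design. A model that conditions on the baseline score removes the part of the follow-up variance that baseline predicts. A two-visit ANOVA uses the baseline only by subtracting it, which is less efficient at any correlation below 1. The FERT model as written does not use it at all.

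Omitting a stratification factor is a smaller matter. The design balances the groups on it, but its variance stays in the error term, so standard errors come out somewhat too large.

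At stake is precision: wider intervals and lower power in a study whose stated purposes include an effect-size estimate for later trials (section 5.3).

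**Working it through.** **The plan's own figure.** The protocol gives no precision figure for these models. Its only related figure is in section 16.1: "This indicates 15-17 participants/group would give 85-90% power to detect a significant group difference at a 0.05 false positive rate", with "we conservatively estimated a smaller effect size (0.5-0.7) for sample size calculation". The stated inputs do not reproduce it: a two-sided two-group t-test with 15-17 per group has 46-51% power at 0.7 and 26-29% at 0.5. That is a separate matter, and nothing below depends on it.

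**Inputs.** From section 16.1: 18 per group, standardised effect 0.5 to 0.7, alpha 0.05 (taken as two-sided). Assumed, because the protocol does not give them: equal variance (set to 1) at both visits, correlation r between 0.3 and 0.7, and gender explaining 10% of variance at each visit.

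**Step 1. Change score against ANCOVA.**

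- Error variance of a change score: 2(1−r).
- Error variance of ANCOVA: 1−r².
- Ratio: 2(1−r)/[(1−r)(1+r)] = 2/(1+r).
- Equivalent sample out of 36: 36 × (1+r)/2.

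| r | Variance ratio | 36 analysed by change are worth |
|---|---|---|
| 0.3 | 1.54 | 23.4 |
| 0.5 | 1.33 | 27 |
| 0.7 | 1.18 | 30.6 |

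**Step 2. Power at 18 per group.** Noncentral t with noncentrality (d/√v) × √(18/2), where v is the error variance from step 1; 34 degrees of freedom for change and 33 for ANCOVA.

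| r | d = 0.5: change, ANCOVA | d = 0.7: change, ANCOVA |
|---|---|---|
| 0.3 | 23%, 33% | 41%, 57% |
| 0.5 | 31%, 39% | 53%, 65% |
| 0.7 | 47%, 53% | 75%, 81% |

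**Step 3. Does the mixed model avoid the loss?** With two visits and complete data, the group-by-time term of an ordinary mixed model compares mean change between groups, as the ANOVA does. It matches ANCOVA only if both groups are given a common baseline mean, which the protocol does not say. So both questionnaire options, as worded, carry the loss. For the cognitive tasks, one of the two options does.

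**Step 4. FERT.** If the group-by-emotion model is fitted to follow-up data alone, the error variance for the between-group comparison is 1 against 1−r² with baseline. The ratio 1/(1−r²) is 1.33 at r = 0.5 and 1.96 at r = 0.7. For a comparison of overall scores at d = 0.7, power is 53% without baseline, against 65% (r = 0.5) or 81% (r = 0.7) with it. Individual emotion contrasts have their own correlations.

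**Step 5. Gender.** Once gender is in the ANCOVA, the variance within gender is 0.9 and the covariance is r−0.1, so the residual variance is 0.9 − (r−0.1)²/0.9.

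- r = 0.5: 0.75 without gender, 0.722 with it; SE ratio √(0.75/0.722) = 1.02.
- r = 0.7: 0.51 without gender, 0.50 with it; SE ratio √(0.51/0.50) = 1.01.

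Simulation of null trials with balanced gender strata gave type I error of about 4.3-4.8% for ANCOVA without gender (r = 0.3 to 0.7), which is slightly conservative. In simulation at d = 0.7, adding gender raised power from 64.5% to 65.8% (r = 0.5) and from 80.3% to 80.7% (r = 0.7).

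**The case against.** The strongest reply is that section 17.1 is only an outline. Sections 16.3.1 and 17 require the analysis to be documented in a SAP that is approved and posted before analysis, and the choice of model and covariates is commonly settled there. This stands against criticism of mere silence. It does not cover what the outline states: a two-visit ANOVA for the questionnaires, and term lists for FERT and the fMRI models that omit the stratum. A SAP that followed the outline faithfully would inherit these.

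The reply also limits the point in three ways, all of which stand. The questionnaire loss falls on secondary outcomes. The primary tasks other than FERT already have ANCOVA as a named option. And the gain from gender is small once baseline is in the model; in a change-score analysis a stable gender effect cancels altogether.

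A reader might infer more from the either/or wording and the optional mood covariates: that the team could choose the more favourable p-value. Picking the smaller of the change-score and ANCOVA p-values after seeing both would give a false-positive rate of roughly 7-8%. The documents do not support that reading, because the SAP must be in place before analysis begins. For the questionnaires the two named options give the same test with complete data, so there is nothing to choose between. The section 12 sentence on covariates is a risk-mitigation remark about pre-treatment measures, not an analysis rule.

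**Conclusion.** The point holds as a loss of precision that can be recovered at almost no cost, not as a threat to the type I error rate.

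- **Questionnaires (secondary):** variance 1.18 to 1.54 times that of ANCOVA for r from 0.7 down to 0.3. The exact ratio depends on r, which the protocol does not give. Only at r close to 1 would the degree of freedom spent on baseline offset the gain.
- **Cognitive tasks other than FERT (primary):** the same loss arises only if the unconstrained mixed model is taken over ANCOVA.
- **FERT (part of the primary battery):** the stated terms leave out baseline and time for a task tested at both visits. This is the firmest case on a primary outcome.
- **Gender:** omission costs about 1-2% in standard error at r of 0.5 to 0.7 with baseline included, assuming 10% of variance explained, and errs on the conservative side.

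**What to change.** In section 17.1, replace both either/or statements with one model for AVLT, N-back, PILT, PLE, PDQ, PHQ-9, GAD-7, SHAPS and the visual analogue scale: follow-up score = group + own baseline score + gender as randomised. If participants with a missing visit are to be kept, use instead a mixed model with a common baseline mean in both groups and gender as a term, which estimates the same effect.

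Add baseline score and gender to the FERT model, and gender to the fMRI group-level models. Limit the mood and PDQ covariates of section 12 to a sensitivity analysis specified in advance. Carry the same wording into the SAP.

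The cost is wording and about two degrees of freedom in the questionnaire comparison (34 to 32). No further participants, visits or measurements are needed.
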